7.2 Adverse Events

Because the investigational intervention is not expected to result in any significant adverse events, adverse event evaluations will be performed at baseline, following each microdose administration, and for 14 days following microdose administration or until all attributed adverse events from the microdose have resolved, whichever is later. Adverse events will be graded accorded to the NCI Common Terminology Criteria for Adverse Events Version 4.0 (CTCAE v4.0). If CTCAE grading does not exist for an adverse event, the severity of mild, moderate, severe, and life-threatening, or grades 1 - 4, will be used. Upon completion of the adverse event assessment window, patients will be followed for efficacy only (see **section 7.3**) until the follow up criteria in **section 6.6** are met.

7.2.1 Adverse Event Definition

Adverse event (AE) means any untoward medical occurrence in a patient or subject administered a pharmaceutical product; the untoward medical occurrence does not necessarily have a causal relationship with this treatment. An AE can therefore be any unfavorable and unintended sign (including an abnormal laboratory finding), symptom, or disease temporally associated with the use of a medicinal (investigational) product whether or not it is related to the medicinal product. This includes any newly occurring event, or a previous condition that has increased in severity or frequency since the administration of study drug.

For this protocol an abnormal laboratory value will not be assessed as an AE unless that value leads to discontinuation or delay in treatment, dose modification, therapeutic

intervention, or is considered by the investigator to be a clinically significant change from baseline.

7.2.2 Serious Adverse Event Definition

Serious adverse event (SAE) means any untoward medical occurrence that at any dose:

- Results in death.
- Is life-threatening (refers to an AE in which the patient was at risk of death at the time of the event. It does not refer to an event which hypothetically might have caused death if it were more severe).
- Requires inpatient hospitalization or prolongation of an existing hospitalization (see clarification below on planned hospitalizations in Section 6.3).
- Results in persistent or significant disability or incapacity. (Disability is defined as a substantial disruption of a person's ability to conduct normal life functions).
- Is a congenital anomaly/birth defect.
- Is a medically important event. This refers to an AE that may not result in death, be immediately life threatening, or require hospitalization, but may be considered serious when, based on appropriate medical judgment, may jeopardize the patient, require medical or surgical intervention to prevent one of the outcomes listed above, or involves suspected transmission via a medicinal product of an infectious agent.
 - Examples of such medical events include allergic bronchospasm requiring intensive treatment in an emergency room or at home, blood dyscrasias or convulsions that do not result in inpatient hospitalization, or the development of drug dependency or drug abuse.
 - With respect to the suspected transmission via a medicinal product of an infectious agent; any organism, virus, or infectious particle (eg, prion protein transmitting Transmissible Spongiform Encephalopathy), whether pathogenic or non-pathogenic, is considered an infectious agent.

Clarification should be made between a serious AE (SAE) and an AE that is considered severe in intensity (Grade 3 or 4), because the terms serious and severe are NOT synonymous. The general term severe is often used to describe the intensity (severity) of a specific event; the event itself, however, may be of relatively minor medical significance (such as a Grade 3 headache). This is NOT the same as serious, which is based on patient/event outcome or action criteria described above and is usually associated with events that pose a threat to a patient's life or ability to function. A severe AE (Grade 3 or 4) does not necessarily need to be considered serious. For example, a white blood cell count of 1000/microL to less than 2000 is considered Grade 3 (severe) but may not be considered serious. Seriousness (not intensity) serves as a guide for defining regulatory reporting obligations.

7.2.3 Reporting Requirements

In addition to completing appropriate demographic and suspect medication information, the report should include the following information within the Event Description of the Medwatch Form 3500A

- Treatment regimen (dosing, frequency, combination therapy)
- Protocol description (include number if assigned)
- Description of event, severity, treatment, and outcome, if known
- Supportive diagnostic and laboratory results
- Investigator's assessment of the relationship of the SAE to each investigational product and suspect medication

7.2.3.1 Follow-up information

Additional information may be added to a previously submitted report by any of the following methods:

- Adding to the original Medwatch Form 3500A and submitting it as follow-up
- Adding supplementary summary information and submitting it as follow-up with the original Medwatch Form 3500A
- Summarizing new information and faxing it with a cover letter including subject identifiers (ie, DOB, initials, subject number), protocol description and number, suspect drug, brief adverse event description, and notation that additional or follow-up information is being submitted

7.2.4 Safety Reporting Requirements for IND

For Investigator Sponsored IND Studies there are some additional reporting requirements for the FDA in accordance with the guidance set forth in 21 CFR 312.32. Sponsor-investigators of studies conducted under an IND must comply with the following safety reporting requirements:

7.2.4.1 Expedited IND Safety Reports

The Sponsor-Investigator is required to report all serious, unexpected and related adverse events directly to the FDA on a MEDWATCH Form 3500A within 7 (if fatal or life-threatening) or 15 calendar days of first awareness.

The Sponsor-Investigator must report in an IND safety report any suspected adverse reaction that is both serious and unexpected (21 CFR 312.32). Before submitting this report, the sponsor needs to ensure that the event meets all three of the definitions contained in the requirement:

- Suspected adverse reaction
- Serious
- Unexpected

If the adverse event does not meet all three of the definitions, it should not be submitted as an expedited IND safety report to the FDA.

The timeframe for submitting an IND safety report to FDA is no later than 15 calendar days after the investigator determines that the suspected adverse event or other information qualifies for reporting.

Any fatal or life-threatening serious, unexpected and related adverse event must be reported to no later than 7 calendar days after initial awareness. Sponsor-Investigators should initially notify FDA by telephone or facsimile transmission. Other means of rapid communication (e.g., email) may also be used, if prior to transmission, the Project Manager in the FDA review division that has responsibility for review of the IND confirms that other means of rapid transmission are acceptable.

Any serious, unexpected and related adverse event that is not fatal or life-threatening must be reported to FDA no later than 15 calendar days after initial awareness.

The Sponsor-Investigator must comply with any applicable requirements related to the reporting of SAEs involving his/her subjects to the IRB that approved the study.

7.2.4.2 IND Annual Reports

In accordance with the regulation 21 CFR 312.33, the Sponsor-Investigator shall within 60 days of the anniversary date that the IND went into effect submit a brief report of the progress of the investigation. Please refer to Code of Federal Regulations, 21 CFR 312.33 for a list of the elements required for the annual report.

7.3 Efficacy Assessments

For the purposes of this study, screening tumor assessments using CT of the chest/abdomen/pelvis and other areas of known disease or newly suspected disease should be performed within 28 days prior to registration. Scans of the abdomen, pelvis and other areas of the body may be done with MRI instead of CT, but evaluation of the chest should be done with CT. CT scans should be performed with iodinated IV contrast and MRI scans with IV gadolinium chelate unless there is a medical contraindication to contrast. If iodinated IV contrast is contraindicated, chest CT should be done without IV contrast. The CT component of a combined PET/CT may be used as long as the slice thickness is < 5 mm.

For the purposes of this study, patients with radiographically measurable disease at baseline should be re-evaluated for response every 8 weeks (+/- 1 week) for 6 months and then every 12 weeks (+/- 2 weeks) thereafter. The interval in imaging may be changed after discussion with the principal investigator. Response and progression will be evaluated in this study using the international criteria proposed by the revised Response Evaluation Criteria in Solid Tumors (RECIST) guideline (version 1.1) [Eur J Ca 45:228-247, 2009]. Changes in the largest diameter (unidimensional measurement) of the tumor lesions and the shortest diameter in the case of malignant lymph nodes are used in the RECIST criteria. Please see **Appendix C** for RECIST 1.1 criteria.

7.4 Dose Modifications

After initiation of treatment in Cycle 1 all dose modifications and delays are at the discretion of the treating investigator according to best medical practices.

8 CRITERIA FOR EVALUATION AND ENDPOINT DEFINITIONS

8.1 Criteria for Evaluation

Evaluable patients will include eligible subjects who receive both the phase 0 and FOLFOX-integrated microdose and have samples collected at least 80% of time points. All patients who receive any component of microdose will be followed for toxicity, but any patient not completing both microdose administrations and 80% of blood samples will be replaced.

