6 STUDY DESIGN AND TREATMENT PLAN

6.1 Study Design

This is a prospective feasibility study of a [¹⁴C]oxaliplatin microdose assay to predict exposure and sensitivity to oxaliplatin as part of standard-of-care FOLFOX chemotherapy. Consenting patients who will be receiving FOLFOX as their treatment for cancer will be enrolled. Patients will receive two [¹⁴C]oxaliplatin microdose infusions over the course of the study. The first part of the study is a Phase 0 [¹⁴C]oxaliplatin microdose infusion occurring over 2 hours and followed by serial blood draws over a 24 hour period for microdose pharmacokinetic and pharmacodynamic analysis (on surrogate peripheral blood mononuclear cells). Between 2 days and 4 weeks after the administration of this phase 0 microdose, patients will begin FOLFOX therapy according to usual care. The initial treatment oxaliplatin dose will be diluted with the same amount of [¹⁴C]oxaliplatin microdose as previously administered. Repeat blood draws for pharmacokinetic assessment of both the microdose and therapeutic dose along with pharmacodynamic analysis on PBMCs will be performed over 46-48 hours (this last draw is timed for the disconnect visit of the 5-FU infusion).

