6.3.3 Sample Collection Schedule

Blood will be collected for pharmacokinetic and pharmacodynamic analysis according to the schedule in **Table 2**. See section 10.1.1 for sample processing.

Table 2. Time Points of Blood Collection for PK Assessment after Phase 0 Microdose

Sample Number	Scheduled time points relative to ^{14}C Oxaliplatin administration		
	Day	Scheduled time	Description
1	1	0-5 min predose	Pre-dose
2	1	30 minutes (± 5 minutes)	Post-dose
3	1	1 hr (± 10 minutes)	Post-dose
4	1	1 hr 45 min (± 10 minutes)	Post-dose
5	1	2 hr (± 10 minutes)	Post-dose
6	1	2 hr 15 min (± 10 minutes)	Post-dose
7	1	3 hr (± 10 minutes)	Post-dose
8	1	4 hr (± 60 minutes)	Post-dose
9	1	24 hr (± 60 minutes)	Post-dose

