8.2 Endpoint Definitions

8.2.1 Primary Endpoint

The primary endpoint is the feasibility of assessing therapeutic pharmacokinetic (PK) parameters of the therapeutic dose using the microdose in evaluable patients. For the purposes of this pilot study, this assessment will be considered feasible if the area under the curve extrapolated to infinity ($AUC_{0\rightarrow\infty}$) of the microdose and the therapeutic dose are within 2-fold of each other when normalized for differences in dose with a 95% confidence interval.

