10.2 Pharmacokinetics

10.2.1 Specimens & Collection Frequency

Blood specimens will be collected at the time points outlined in **Table 2** and **Table 3**.

Plasma will be used for PK assessment. Since a very small fraction of oxaliplatin is metabolized at the terminal phase, we will not determine the terminal half-lives if they are longer than 24 hours.

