11.2 Analysis Plan

11.2.1 Primary Analyses

For the primary endpoint of feasibility is defined in **section 8.2.1**. We will correlate dose normalized $\text{AUC}_{0-\infty}$ parameters from phase 0 microdosing with parameters from the therapeutic dose of oxaliplatin for evaluable patients (the criteria for evaluation are listed in **section 8.1**). While assessment of PK feasibility is the primary endpoint of this study, we will use the totality of the data, including assessment of DNA adduct formation in PBMCs to determine the future development of this assay.

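### The 80% sample rule accepts patients with no draw after 4 h, although the primary AUC0–∞ depends on those draws

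*Combined protocol and SAP*

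**What the plan says.** - **Evaluability (8.1).** Besides receiving both microdoses, a patient must "have samples collected at least 80% of time points". The consequence of failing is that "any patient not completing both microdose administrations and 80% of blood samples will be replaced". No time point is mandatory, and the text does not say whether 80% is counted per occasion or over both.
- **Primary endpoint (8.2.1, 11.2.1).** "this assessment will be considered feasible if the area under the curve extrapolated to infinity" of the microdose and of the therapeutic dose, after dose normalisation, agree within 2-fold with a 95% confidence interval. The analysis compares phase 0 "with parameters from the therapeutic dose of oxaliplatin for evaluable patients".
- **Sampling (6.1, Tables 2 and 3).** The phase 0 infusion is "followed by serial blood draws over a 24 hour period for microdose pharmacokinetic" and pharmacodynamic analysis: nine points, of which only the 24 h draw comes after 4 h. Cycle 1 has the same nine plus 48 h, and "this last draw is timed for the disconnect visit of the 5-FU infusion".
- **Extrapolation (10.2, 11.2).** The only statement on the terminal phase is that "we will not determine the terminal half-lives if they are longer than 24 hours". That is a limit on reporting a half-life. It does not say which points give the slope, how AUC0–∞ is then obtained, or what happens when a late sample is missing.

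**The concern.** AUC0–∞ adds to the measured area a tail equal to the last concentration divided by the terminal slope. Section 2.2 gives half-lives of 25.8 minutes, 16.8 hours and 391 hours. After a 2 h infusion, samples that stop at 4 h mostly see the fast phase, so a slope fitted to them is far too steep and most of the 16.8 h phase is lost. If this happens on one occasion only, the within-patient ratio moves although nothing pharmacokinetic differs. With six patients, one such ratio shifts the mean and widens the interval.

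A smaller, related matter is that phase 0 ends at 24 h and cycle 1 at 48 h, with no rule on a common slope. The same true curve can then give different AUC0–∞ and t1/2 on the two occasions.

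**Working it through.** **1. The plan's own figure.** Section 11.3 wants 80% probability that a 95% CI for the geometric mean ratio lies within 0.5–2, and states n = 6. Read the quoted CVs (0.3–0.5) as CVs of the ratio. Log SD = √ln(1 + CV²) = 0.294, 0.385, 0.472 for CV 0.3, 0.4, 0.5. The criterion is mean log ratio ± t(0.975, 5 df) × SD/√6 inside ±ln 2. Simulated probability at n = 6 with no true difference: 99%, 87%, 66%. The smallest n reaching 80% is 5, 6 and 8, so n = 6 is reproduced in the middle of the range.

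**2. Counts (no assumptions).**
- Phase 0 without 24 h: 8/9 = 89%.
- Cycle 1 without 24 h and 48 h: 8/10 = 80%.
- All three missing, pooled: 0.8 × 19 = 15.2, so 16 are needed; 16/19 = 84%.

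On either reading of the denominator, a patient with no sample after 4 h passes.

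**3. Effect on one patient's ratio.** Assumptions:
- a noise-free three-phase curve with the documents' half-lives;
- a 2 h infusion (6.3.1), with times counted from its start, which the 1 h 45 min, 2 h and 2 h 15 min draws suggest;
- identical pharmacokinetics on both occasions;
- linear-up/log-down area plus C_last/slope;
- missing late samples handled by extrapolating from 4 h, on which the plan is silent.

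The documents do not give the share of AUC in the middle phase, so it is varied over 20–60%. The upper end comes from section 2.2, where about half the drug is in urine by 6 h. If excretion tracks exposure, AUC0–6 should be about half the total or more. In the model it is 84%, 71%, 59% and 51% at shares of 20, 35, 50 and 60%.

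Results with a three-point slope and no terminal phase (estimated AUC0–∞ relative to truth = 1):

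| Middle share | Phase 0, complete (a) | Any occasion ending at 4 h (b) | Cycle 1, complete (c) | Complete c/a | Phase 0 lacks 24 h: c/b | Cycle 1 lacks both: b/a |
|---|---|---|---|---|---|---|
| 20% | 1.024 | 0.817 | 1.066 | 1.04 | 1.30 | 0.80 |
| 35% | 0.989 | 0.694 | 1.056 | 1.07 | 1.52 | 0.70 |
| 50% | 0.960 | 0.573 | 1.045 | 1.09 | 1.82 | 0.60 |
| 60% | 0.946 | 0.493 | 1.036 | 1.10 | 2.10 | 0.52 |

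A two-point slope or a terminal phase of up to 10% of AUC changes these little: about 1.3–2.1 and 0.8–0.5 overall. If the tables count from the end of infusion, the missing-sample ratios are about 1.3–1.9 and 0.8–0.5. Percent extrapolated would not expose such a patient: it is 2–10% at shares up to 65%, no higher than in a complete phase 0 profile.

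**4. Effect on the criterion.** n = 6, five complete patients at about 1.05, and one without the phase 0 24 h sample at 1.3 to 2.1:

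| Ratio CV | No bias | One such patient |
|---|---|---|
| 0.3 | 99% | 97–75% |
| 0.4 | 87% | 83–57% |
| 0.5 | 66% | 61–41% |

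If the five complete patients sit at 1.10 instead, the lower ends become about 70%, 52% and 38%.

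**5. Complete samples.** The schedule difference alone gives an AUC0–∞ ratio of about 1.03–1.10 (1.00–1.04 if timed from the end of infusion). As a within-patient CV this is ln(1.03)/√2 = 2% to ln(1.10)/√2 = 7%. The t1/2 ratio is larger: about 1.4–2.5 at these shares (1.00–1.26 from the end of infusion).

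**The case against.** The harm is conditional twice: a late draw must be missed, and the analyst must extrapolate from 4 h. Section 9 does schedule the phase 0 Day 2 draws, and nothing in the documents says they will be missed. A compartmental fit, which section 10.2.2 does not exclude, would behave differently. This is a pilot, and section 11.2.1 lets the totality of the data guide further development. At a ratio CV of 0.3 the probability stays above 80% unless the middle share nears 60%; at 50% it is 83%. The half-lives are given in 3.1.4.2 for ultrafilterable platinum, while 10.1.1 and 10.2.2 count ¹⁴C in plasma (2.5 says ultrafiltrate), so the modelled sizes may not carry over.

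All of this limits the size. None of it alters the counts or supplies the missing rule, and with six patients a slope or exclusion chosen after seeing the data could decide the result.

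A reader might go further in three ways that the documents do not support:
- *The 24 h versus 48 h schedules endanger the primary criterion, or must give different AUCs.* With complete samples the mismatch is at most about 10% against a 2-fold margin, and it can vanish with another time origin or fitting method.
- *One missing draw can give a ratio near 3.* That needs a middle share of about 85%, which fits poorly with the urinary figure in 2.2.
- *The rule could falsely establish feasibility.* The modelled error mainly makes feasibility harder to declare.

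**Conclusion.** The concern holds for the evaluability rule. Section 8.1 accepts, and does not replace, patients whose primary parameter cannot be reliably estimated, and no other section repairs this. Under the stated model, one such patient of six lacking the phase 0 24 h draw costs between about 2 and 30 percentage points of the probability of success, depending on the ratio CV and on a phase share that the documents do not give.

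The schedule mismatch is secondary. It does not threaten the 2-fold criterion. It does blur the descriptive phase 0 versus cycle 1 comparison (8.2.2.2, 11.2.2.2) behind objective 1.2.2, because an artefact of 2–7% is as large as the under-5% target.

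Severity is minor to should-fix. Confidence is high on the counts and medium on the sizes.

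**What to change.** - **8.1:** require the 24 h sample on both occasions in addition to the 80% count, and apply the 80% per occasion.
- **10.2 and 11.2:** compute AUC0–∞ and t1/2 on both occasions from the shared 0–24 h times, with one prespecified terminal-slope rule and actual sampling times. Keep AUC0–∞ as primary. Report the AUC0–24 ratio as supportive, and the AUC0–∞ that uses the 48 h sample as a sensitivity analysis.

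Both parts are needed. A shared slope rule alone leaves a patient without the phase 0 24 h draw at a/b, for example 0.960/0.573 = 1.68 at a 50% share. The 24 h requirement alone leaves the 1.03–1.10 mismatch. With both, the modelled ratio is 1.00 at every share, although draws spread over the allowed windows still scatter a single patient's ratio (0.83–1.22 with actual times).

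This is a cheap improvement: wording only, with no new draws. The costs are an occasional extra replacement through the mechanism 8.1 already has (including a patient who lacks only the cycle 1 24 h draw), a 48 h sample that no longer enters the primary ratio, and a half-life that is understated about equally on both occasions (5.3–9.5 h in the model with the 3, 4 and 24 h points, against 16.8 h).

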8.2 Endpoint Definitions

8.2.1 Primary Endpoint

The primary endpoint is the feasibility of assessing therapeutic pharmacokinetic (PK) parameters of the therapeutic dose using the microdose in evaluable patients. For the purposes of this pilot study, this assessment will be considered feasible if the area under the curve extrapolated to infinity ($AUC_{0\rightarrow\infty}$) of the microdose and the therapeutic dose are within 2-fold of each other when normalized for differences in dose with a 95% confidence interval.

8.2.1.1 Justification of the primary endpoint

Prior microdosing work suggests that a close relationship between multiple microdose and full dose pharmacokinetic parameters including $t_{1/2}$ and AUC can be observed [77]. In this study, we have chosen to focus on total exposure to treatment as total exposure is related to the primary dose limiting toxicity of oxaliplatin treatment (i.e. peripheral neuropathy) [81]. While a close relationship will be required for final development, a relationship within 2-fold will provide sufficient preliminary data to suggest that further development and optimization of the assay will be warranted.

8.2.2 Secondary Endpoints

Secondary endpoints include:

- 8.2.2.1 Assessment of other PK parameters (e.g. C_{max} , t_{max} , $t_{1/2}$, CL) of the phase 0 microdose compared to the therapeutic dose.
- 8.2.2.2 Comparison of the PK parameters of the phase 0 microdose to the FOLFOX-integrated microdose.
- 8.2.2.3 The association of oxaliplatin-DNA adducts (see **section 10.3**) and tumor response by RECIST 1.1 (see **Appendix C**).
- 8.2.2.4 The association of oxaliplatin-DNA adducts (see **section 10.3**) and duration of disease control (see **Appendix C**).
- 8.2.2.5 Safety according to the Common Terminology Criteria for Adverse Events version 4 (see **section 7.2**).

